6.3. Planned Dose Adjustments

No pre-specified dose adjustments are planned in the first influenza season. Dose adjustments of OSV may be made as indicated in the prescribing information. Samples taken for PK analysis are planned to be analyzed during the study. Following the availability of the PK results sites will be informed if any dosing changes are to be made. Dose adjustments may also be determined following the IDMC review of safety data. Further details will be provided in the IDMC charter.

6.4. Blinding

This will be a double-blind study for the investigational product and both study staff and the subject will remain blinded to the investigational treatment. However, there will be qualified personnel at each study site who will be unblinded to allow preparation of study medication. Unblinding of GSK to the aggregated summary results by treatment group of the interim analyses is addressed in the IDMC charter.

The GSK team members will not have access to subject specific treatment assignment so as to not potentially introduce bias in discussions with the study center.

During the blinded randomized treatment period, subjects will receive an intravenous infusion (DNX or placebo) twice daily plus open label OSV oral therapy twice daily.

- IV infusion: Unblinded personnel will prepare an IV infusion of active DNX (15 mg FBE or 50 mg FBE) or normal saline infusion for each subject twice daily.
- Oral therapy: Qualified personnel will prepare the open-label oral oseltamivir therapy for each subject twice daily.
- The investigator or treating physician may unblind a subject's treatment assignment **only in the case of an emergency** OR in the event of a serious medical condition when knowledge of the study treatment is essential for the appropriate clinical management or welfare of the subject as judged by the investigator.
- Investigators have direct access to the subject's individual study treatment.
- It is preferred (but not required) that the investigator first contacts the Medical Monitor or appropriate GSK study personnel to discuss options **before** unblinding the subject's treatment assignment.

- If GSK personnel are not contacted before the unblinding, the investigator must notify GSK as soon as possible after unblinding, but without revealing the treatment assignment of the unblinded subject, unless that information is important for the safety of subjects currently in the study.
- The date and reason for the unblinding must be fully documented in the case report form (CRF).

A subject will be withdrawn if the subject's treatment code is unblinded by the investigator or treating physician. The primary reason for discontinuation (the event or condition which led to the unblinding) will be recorded in the CRF.

- GSK's Global Clinical Safety and Pharmacovigilance (GCSP) staff may unblind the treatment assignment for any subject with an SAE. If the SAE requires that an expedited regulatory report be sent to one or more regulatory agencies, a copy of the report, identifying the subject's treatment assignment, may be sent to investigators in accordance with local regulations and/or GSK policy.

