5.4. Withdrawal/Stopping Criteria

A subject is considered to be withdrawn prematurely from the study if they do not complete the Day 45 Visit.

Criteria for premature study withdrawal include:

- Adverse event
- protocol deviation
- non-compliance
- subject lost to follow up
- subject withdraws consent
- investigator discretion
- sponsor terminates the study

The following actions must be taken in relation to a subject who fails to attend the clinic for a required study visit:

- The site must attempt to contact the subject and re-schedule the missed visit as soon as possible.
- The site must counsel the subject on the importance of maintaining the assigned visit schedule and ascertain whether or not the subject wishes to and/or should continue in the study.
- In cases where the subject is deemed ‘lost to follow up’, the investigator or designee must make every effort to regain contact with the subject (where possible, 3 telephone calls and if necessary a certified letter to the subject’s last known mailing address or local equivalent methods). These contact attempts should be documented in the subject’s medical record.
- Should the subject continue to be unreachable, only then will he/she be considered to have withdrawn from the study with a primary reason of “Lost to Follow-up”.

A subject may withdraw from study treatment at any time at his/her own request, or may be withdrawn at any time at the discretion of the investigator for safety, behavioral or administrative reasons. If a subject withdraws from the study, he/she may request destruction of any samples taken, and the investigator must document this in the site study records.

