5.4.1. Premature Discontinuation of Investigational Product

A subject is considered to have prematurely discontinued investigational product (IP) if they have not completed 5 days of randomized treatment (not applicable for subjects discharged from the hospital due to symptom improvement).

If a subject is prematurely discontinued from IP, the investigator must make every effort to perform all the remaining study visits as described in the Time and Events Table, including the final Day 45 Visit.

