5.4.4. Other Stopping Criteria

Subjects should be permanently discontinued from IP if any of the following conditions are met:

- Serum creatinine: 0.5 mg/dL increase from baseline, on 2 successive readings;
- eGFR of <60 on two consecutive readings using the CKD-EPI calculation (eGFR of <30 for moderate renal impairment);
- Peripheral neutropenia: absolute neutrophil counts <0.5 Gi/L on 2 successive assessments.

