The clinical response based on vital signs/ventilation status requires 24-hour confirmation. Considering 2-hour assessment window, the response confirmation period is 22 hours, i.e. all assessments within 22 hours of the initial response and at least one at or beyond 22 hours need to meet the criteria in order for the response to be confirmed. Any missing scheduled assessment will be imputed with response value of 0 (1 means response). Only hospital discharge due to clinical response or a confirmed response based on vital signs/ventilation criteria is considered as event for the TTCR analysis. Hospital discharge due to clinical improvement can serve as 24-hour confirmation for the clinical response and the event date should be the onset of the vital signs response. Subjects who died prior to achieving a clinical response will be assigned a worst value of TTCR (99 days). All other subjects who did not achieve a confirmed response will be censored at the last assessment date of vital signs.

For further details of the calculation of TTCR see Section 11.6.4.

Model Specification

Not applicable

Model Checking & Diagnostics

Not applicable

Model Results Presentation

Not applicable

Sensitivity and Supportive Statistical Analyses

 No sensitivity analyses or subgroup analyses will be performed given the small number of subjects.

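### The code-break and study-withdrawal rules are not separated from stopping IP, so follow-up to Day 45 can end in subjects selected by clinical deterioration

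*Protocol*

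**What the plan says.** **Code break.** Protocol 6.4 makes withdrawal mandatory when the "treatment code is unblinded by the investigator or treating physician". It names neither IP nor study. The next sentence is "The primary reason for discontinuation (the event or condition which led to the unblinding) will be recorded in the CRF". Section 6.4 gives no follow-up instruction. A code break is allowed only in an emergency or "in the event of a serious medical condition when knowledge of the study treatment is essential".

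**Leaving the study.** Protocol 5.4: "A subject is considered to be withdrawn prematurely from the study if they do not complete the Day 45 Visit". Under "Criteria for premature study withdrawal include" it then lists adverse event, protocol deviation, non-compliance, loss to follow-up, withdrawn consent, investigator discretion and sponsor termination.

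**Stopping IP.** After premature IP discontinuation, 5.4.1 says "the investigator must make every effort to perform all the remaining study visits as described in the Time and Events Table", and it names the Day 45 Visit. The renal and neutrophil rules in 5.4.4 are IP rules: "Subjects should be permanently discontinued from IP if any of the following conditions are met". The liver and QTc rules (5.4.2, 5.4.3) also stop IP, not participation.

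**Analysis.** SAP 7.1.2 gives deaths before response a TTCR of 99 days. It then says: "All other subjects who did not achieve a confirmed response will be censored at the last assessment date of vital signs". SAP 11.7.2.3 labels the primary approach Discontinuation=Failure, says that it covers subjects who left early, and refers back to 7.1.2.

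**The concern.** A code break needs an emergency or a serious condition, so the rule acts on subjects who are doing badly. An adverse event listed as a study-withdrawal criterion can act the same way. If such a subject leaves the study, the later course that decides TTCR, TTRR and most secondary endpoints goes unobserved.

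Treating that subject as censored assumes the same chance of later response as subjects still under observation. Withdrawal triggered by deterioration makes this doubtful. If such withdrawals were more frequent on one arm, the treatment comparison could shift. In a first study of DNX in hospitalised influenza, the direction that matters most is harm being hidden.

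**Working it through.** The plan states no withdrawal or code-break rate, so there is no figure of its own to reproduce. The check is a comparison of the texts, followed by an illustration with assumed rates.

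**1. What withdrawal means in 6.4.** Usage elsewhere points both ways.
- Towards study exit: the protocol usually names IP when it means IP (the neutrophil row of 4.6.1; 5.4.3; 5.4.4). Section 12.6.2 sets stopping medication apart from leaving the study.
- Towards IP only: the follow-on sentence in 6.4 speaks of discontinuation. The renal row of 4.6.1 uses the same verb for subjects who meet the renal stopping criteria, which in 5.4.4 stop IP.

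If IP is meant, 5.4.1 applies and follow-up continues. If the study is meant, follow-up stops. A site cannot tell which from the text. Section 5.4 refers expressly to the study.

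**2. What a study exit would lose.** Vital signs and respiratory status three times daily in hospital (7.3.3), ICU and discharge dates, and the Day 45 visit. It would not lose follow-up of SAEs and AESIs (7.4.1.3) or data already collected (SAP 11.7.1). A death counts as 99 days only if it is captured.

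**3. How many subjects.** Assume a code-break rate of 1% to 5%, with every code break a study exit.
- Planned trial: 0.01 × 300 = 3; 0.05 × 300 = 15.
- Enrolled: 0.01 × 10 = 0.1; 0.05 × 10 = 0.5.

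**4. Effect on the hazard ratio (illustration).**

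Inputs from protocol 9.2.1: control hazard λ = 0.83 and median 5.8 days. These agree if λ is per week: ln 2 / (5.8/7) = 0.837, and 0.83 gives a median of 7 × ln 2 / 0.83 = 5.85 days.

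Assumptions: no drug effect in subjects who stay; a fraction w of an arm withdraws at Day 2; none of these would have responded by Day 45. The last assumption is deliberately extreme.

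Let F = 45/7 = 6.429 weeks, c = 2/7 = 0.286 weeks and q = 1 − exp(−λF) = 0.9952, so q/λ = 1.199. The hazard is events divided by time at risk:
- followed to Day 45: (1−w)q / [(1−w)q/λ + wF]
- censored at Day 2: (1−w)q / [(1−w)q/λ + wc]

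| w | Followed | Censored |
|---|---|---|
| 2% | 0.975/1.304 = 0.748 | 0.975/1.181 = 0.826 |
| 5% | 0.945/1.460 = 0.647 | 0.945/1.153 = 0.820 |
| 10% | 0.896/1.722 = 0.520 | 0.896/1.108 = 0.809 |
| 15% | 0.846/1.983 = 0.426 | 0.846/1.062 = 0.797 |

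Hazard ratios, DNX over control (below 1 means slower response on DNX):

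| Withdrawn, DNX vs control | HR if followed | HR if censored |
|---|---|---|
| 5% vs 5% | 1.00 | 1.00 |
| 5% vs 2% | 0.87 | 0.99 |
| 10% vs 5% | 0.80 | 0.99 |
| 15% vs 5% | 0.66 | 0.97 |

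With equal rates and no drug effect, nothing shifts. With unequal rates, censoring brings the ratio back close to 1.

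**5. The SAP's two rules.** Section 7.1.2, repeated in 11.6.4, censors a living non-responder at last vital signs, so a subject who leaves on Day 2 carries information to Day 2 only. A rule that counts discontinuation as failure would keep that subject as a non-responder. The two treat the same subject differently, and 11.7.2.3 cites 7.1.2 as its source.

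**The case against.** The strongest case against is that this is a small wording gap.
- Section 6.4 can be read as IP only, and 5.4.1 then protects follow-up.
- The 5.4 list mixes in loss to follow-up, withdrawn consent and sponsor termination. It therefore reads as a list of recorded reasons rather than instructions to remove subjects.
- The specific safety rules stop IP only, and Appendix 2 lets a subject with a liver stopping event stay for follow-up assessments.
- SAEs and AESIs are followed regardless, and censored subjects still contribute time at risk.
- The SAP summarises reasons for censoring (11.6.4) and lists study withdrawals and broken blinds (11.13.18), so any loss would be visible.
- The censoring rule belongs to a descriptive SAP for 10 subjects. The protocol's 300-subject Bayesian analysis states no censoring rule.

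Most of this stands as a limit on the claim. A reader might infer that outcome and safety data are certain to be lost in the sickest subjects. The documents do not support that: 6.4 is ambiguous, safety follow-up is largely preserved, and SAP 11.7.2.3 leaves even the censoring unsettled. Nor do they show that withdrawal would differ by arm.

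What remains is that 6.4 is mandatory, is triggered by serious illness and carries no retention clause, and that 5.4 refers to the study. SAE and AESI follow-up does not replace the vital-sign, oxygen and discharge records on which TTCR rests.

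**Conclusion.** The point holds as an inconsistency with a real but conditional risk. As written, 6.4 and 5.4 permit study exit, and 6.4 on one reading requires it, for reasons tied to clinical course. That runs against the retention intent of 5.4.1. Censoring such subjects at last vital signs is potentially informative.

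The size is unknown because no rate is given. Under the stated assumptions, 3 to 15 of 300 planned subjects would be affected. Unequal withdrawal (5% vs 2% up to 15% vs 5%) would turn ratios of 0.87 to 0.66 into 0.99 to 0.97. These figures need both unequal rates and no later response among those withdrawn, and they cover only the case of no drug effect in the remaining subjects. For the report actually planned, with 10 subjects and no hypothesis test, the effect is small.

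**What to change.** 1. **Protocol 6.4:** state that a code break is documented and is not in itself a reason to end study follow-up. Scheduled assessments continue to Day 45 unless consent is withdrawn or the subject is lost to follow-up.
2. **Protocol 5.4:** reconcile with 5.4.1 so that leaving the study is kept separate from stopping IP. No IP-stopping rule changes, and decisions on IP stay as the sponsor has set them.
3. **SAP 7.1.2, 11.6.4 and 11.7.2.3:** settle on one rule for living non-responders who leave early, and state it the same way in each place.

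The cost is wording, plus visits already on the schedule continuing for a few subjects.

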6.5. Packaging and Labeling

The contents of the label will be in accordance with all applicable regulatory requirements.

6.6. Preparation/Handling/Storage/Accountability

A description of the methods and materials required for preparation of 15 mg FBE IV DNX, 50 mg FBE IV DNX and IV DNX placebo will be detailed in a Study Specific Technical Agreement/Memo (TTS) or Pharmacy Manual which will be accompanied by a Quality Agreement.

- The investigator or designee must confirm appropriate temperature conditions have been maintained during transit for all study treatment received and any discrepancies are reported and resolved before use of the study treatment.
- Only subjects enrolled in the study may receive study treatment and only authorized site staff may supply or administer study treatment. All study treatments must be stored in a secure environmentally controlled and monitored (manual or automated) area in accordance with the labelled storage conditions with access limited to the investigator and authorized site staff.
- The investigator, institution, or the head of the medical institution (where applicable) is responsible for study treatment accountability, reconciliation, and record maintenance (i.e. receipt, reconciliation and final disposition records).
- Further guidance and information for final disposition of unused study treatment are provided in the SRM.
- Under normal conditions of handling and administration, study treatment is not expected to pose significant safety risks to site staff. Take adequate precautions to avoid direct eye or skin contact and the generation of aerosols or mists. In the case of

unintentional occupational exposure notify the monitor, Medical Monitor and/or GSK study contact.

- A Material Safety Data Sheet (MSDS)/equivalent document describing occupational hazards and recommended handling precautions either will be provided to the investigator, where this is required by local laws, or is available upon request from GSK.

6.7. Compliance with Study Treatment Administration

Subjects will receive study treatment directly from the investigator or designee, under medical supervision. The date and time of each dose administered in the clinic will be recorded in the source documents. The study subject identification will be confirmed at the time of dosing by a member of the study site staff other than the person administering the study treatment.

15 mg FBE DNX, 50 mg FBE DNX and DNX placebo will be intravenously administered to subjects at the site.

Open label 75 mg OSV will be provided for oral administration by the investigator or designee to all subjects.

Administration will be documented in the source documents and reported in the CRF.

6.8. Treatment of Study IP Overdose

GSK does not recommend specific treatment for an overdose.

In the event of an overdose the investigator or treating physician should:

- contact the Medical Monitor immediately
- closely monitor the subject for adverse events (AEs)/serious adverse events (SAEs) and laboratory abnormalities until IP can no longer be detected systemically (at least 3 days for IP)
- obtain a blood sample for pharmacokinetic (PK) analysis within 48 hours from the date of the last dose of study treatment if requested by the Medical Monitor (determined on a case-by-case basis). PK sample may not be required for subjects known to be receiving placebo or non-GSK comparator treatments. Record the date/time of the PK blood sample draw and the date/time of the last dose of study treatment prior to blood sample draw on the eCRF. If the date or time of the last dose is unclear, provide the subject's best approximation. If the date/time of the last dose cannot be approximated OR a PK sample cannot be collected in the time period indicated above, do not obtain a PK sample. Instructions for sample handling and shipping are in the SRM.
- document the quantity of the excess dose as well as the duration of the overdosing in the CRF.

Decisions regarding dose interruptions or modifications will be made by the investigator in consultation with the Medical Monitor based on the clinical evaluation of the subject.

6.9. Treatment after the End of the Study

Subjects will not receive any additional treatment from GSK after completion of the study because currently the investigational medication is for acute treatment in the hospital and this is the first study evaluating efficacy and safety of IV DNX in subjects hospitalized for influenza.

The investigator is responsible for ensuring that consideration has been given to the post-study care of the subject's medical condition, whether or not GSK is providing specific post-study treatment.

6.10. Lifestyle and/or Dietary Restrictions

6.10.1. Dietary Restrictions

- Subjects who use tobacco products will be allowed to take part, as long as they refrain from smoking for the duration of the hospitalization, but use of nicotine containing products will be recorded;
- Subjects should abstain from consuming alcohol for the duration of hospitalization.

6.11. Concomitant Medications and Non-Drug Therapies

6.11.1. Permitted Medications and Non-Drug Therapies

In general, concomitant medications (prescription and non-prescription) will be permitted during the study at the investigator's discretion (except for prohibited medications described in Section 6.11.2) and should be administered only as medically necessary during the study. All concomitant medications taken during the study will be recorded in the eCRF. The minimum requirement is that the drug name, dates and times of administration are to be recorded.

6.11.2. Prohibited Medications and Non-Drug Therapies

The only approved antiviral drug permitted during the study is 75 mg OSV. All other approved or investigational influenza antiviral drugs are not permitted during the study (i.e. zanamivir, peramivir, laninamivir, amantadine, rimantadine, ribavirin, vitaglutam, umifenovir).

Immunosuppressive medications are prohibited during the treatment period including but not limited to rituximab, alkylating agents such as cyclophosphamide, nitrosoureas, platinum compounds; purine analogs such as fluorouracil; cytotoxic antibiotics such as dactinomycin, anthracyclines, mitomycin C, bleomycin, mithramycin.

Immunoglobulins are prohibited during the treatment period.

7. STUDY ASSESSMENTS AND PROCEDURES

Protocol waivers or exemptions are not allowed with the exception of immediate safety concerns. Therefore, adherence to the study design requirements, including those specified in the Time and Events Table, are essential and required for study conduct.

This section lists the procedures and parameters of each planned study assessment. The exact timing of each assessment is listed in the Time and Events Table Section [7.1](#)

The following points must be noted:

- If assessments are scheduled for the same nominal time, THEN the assessments should occur in the following order:
 1. 12-lead ECG
 2. vital signs
 3. blood draws.

Note: The timing of the assessments should allow the blood draw to occur at the exact nominal time.

- The timing and number of planned study assessments, including safety, pharmacokinetic, biomarker or virological assessments may be altered during the course of the study based on newly available data (e.g., to obtain data closer to the time of peak plasma concentrations) to ensure appropriate monitoring.
- The change in timing or addition of time points for any planned study assessments must be documented in a Note to File which is approved by the relevant GSK study team member and then archived in the study sponsor and site study files, but this will not constitute a protocol amendment.
- The IRB/IEC will be informed of any safety issues that require alteration of the safety monitoring scheme or amendment of the Informed Consent Form.
- No more than 500 mL of blood will be collected over the duration of the study for study assessments, including any extra study assessments that may be required.

7.1. Time and Events Table

Table 3 Time and Events Table: Assessments at Baseline and During Treatment

Procedures	Eligibility Assessments	During Treatment - 5 days ^a Inpatient						Post-treatment (PT) Inpatient
		Baseline/ Study Day 1 ^a	Study Day 2	Study Day 3	Study Day 4	Study Day 5 /day of last dose ^a	Study Day 6 if applicable ^b	
Written informed consent	X	X						
Subject demography	X	X						
Physical examination ^c		X	X	X	X	X	X	Daily
Influenza Test – locally performed (equipment provided by GSK)	X	X						
Medical/Prior Medication/Drug/Smoking History	X	X						
HIV and Liver Disease History ^d	X	X						
Influenza symptoms ^e	X	X						
HIV, Hep B and Hep C Test ^f	X	X						
Chronic underlying illness assessment	X	X						
Inclusion/Exclusion Criteria	X							
Safety/Efficacy Assessments								
Chest X-ray ^g		X						
ECG ^h	X	X				X	X	
Adverse events		X	X	X	X	X	X	Daily
Concomitant medications ⁱ		X	X	X	X	X	X	Daily
Complications of influenza/associated antibiotic use ^j		X	X	X	X	X	X	Daily
Vital signs (temperature, HR, BP, respiratory rate, oxygen saturation, ventilation status) ^k	X	X	X	X	X	X	X	3 x Daily
Flu PRO		X	X	X	X	X	X	Daily
Katz Activities of Daily Living ^l		X	X	X	X	X	X	Daily
Activity level ^m		X	X	X	X	X	X	Daily
Laboratory Assessments								

Procedures	Eligibility Assessments	During Treatment - 5 days ^a Inpatient						Post-treatment (PT) Inpatient
		Baseline/ Study Day 1 ^a	Study Day 2	Study Day 3	Study Day 4	Study Day 5 /day of last dose ^a	Study Day 6 if applicable ^b	
Chemistry including Liver Function Tests (Local+Central) ⁿ	X	X		X		X	X	Day 6,7,8
Serum creatinine (Local+Central) ^o	X	X	X	X	X	X	X	Day 6,7,8
Hematology (Local+Central) ^p	X	X		X		X	X	Day 6,7,8
Urine Output ^q		X	X	X	X	X	X	
Pregnancy test ^r	X	X						PT Day 3
Nasopharyngeal swab ^s		X		X		X	X	Day 8,12,16,20,24,28,32
Nasal Swab ^t	X	X						
BAL ^u		X		X		X	X	
Endotracheal aspirate ^v		X		X		X	X	Day 8,16,24,32, 45
Nasal SAM strips (biomarkers) ^w		X		X		X	X	Day 8,16,24,32, discharge or Day 45
Nasal washes ^x		X		X		X	X	Day 8,16,24,32, discharge or Day 45
Exploratory Biomarkers (Blood Sample)		X		X		X	X	Day 8,16,24,32, discharge or Day 45
PK sample (Dried Blood Spot) ^y		X		X		X	X	
Genetics Sample (Blood Sample) ^z		X						
Transcriptomics (Blood Sample) ^z		X		X		X	X	Day 8, 16, 24, 32, discharge or Day 45

Procedures	Eligibility Assessments	During Treatment - 5 days ^a Inpatient						Post-treatment (PT) Inpatient
		Baseline/ Study Day 1 ^a	Study Day 2	Study Day 3	Study Day 4	Study Day 5 /day of last dose ^a	Study Day 6 if applicable ^b	
Study Treatments								
Administration of investigational medication (IV) and oseltamivir (oral) twice daily		X	X	X	X	X	X	

- a. A 'Day' is defined as a 24 hour period (Treatment Day), therefore depending on the start time of the first dose of IV DNX, a Treatment Day may span two calendar days.
- b. Day 6 assessments only applicable if last day of dose of randomized treatment is on Day 6 (i.e for subjects who received first dose after 12 noon on Baseline/Day 1.
- c. Physical exam to be performed twice daily for subjects in the sentine cohort.
- d. Enrollment into the study will be based on history of diagnosis of HIV and liver disease. Blood samples will be analyzed after enrollment to retrospectively determine if subject is HIV, Hep B or Hep C positive; however, results will not be available until after completion of dosing.
- e. Influenza symptoms to be assessed only at baseline for inclusion.
- f. Enrollment into the study will be based on any history of diagnosis of HIV and liver disease.
- g. Chest X-ray at Baseline and whenever clinically indicated.
- h. ECG: For the ECG on Baseline/Day 1, one 12-lead ECG (can be done within approximately 24 hours prior to dosing). At Baseline and on Day 5 or last treatment day, a monitoring strip can be utilized if a 12-lead ECG cannot be performed.
- i. Concomitant medications for influenza treatment of the current episode to be recorded from Day -7 (i.e. one week prior to baseline), if available.
- j. Complications of influenza such as bacterial pneumonia, pneumothorax, pleural effusion, ARDS, myositis, encephalitis, myocarditis, and associated antibiotic use will be recorded on all assessment days.
- k. Vital signs and ventilation status to be assessed three times daily during the treatment period between approximately 8 AM and 8 PM.
- l. Katz ADL score collected once daily while hospitalized.
- m. Activity level to be recorded as one of three responses (bed rest, limited ambulation or unrestricted) everyday while hospitalized
- n. Chemistry panel including Liver Function Tests to be required once every other day during treatment (local testing (L) of LFTs for subject management as well as central laboratory testing (C)).
- o. Serum creatinine level required at Baseline and twice daily during treatment for subjects in the sentinel cohort. For all other subjects, serum creatinine level required at Baseline and once daily during treatment (local testing (L) for subject management as well as central testing(C)).
- p. Hematology panel including CBC with differential required every other day during treatment (local testing (L) for subject management as well as central testing(C))
- q. Urine output to be measured twice daily for subjects in the sentinel cohort.
- r. Ultrasensitive urine or blood pregnancy test required in women of childbearing potential prior to dosing and 3 days post last dose of study treatment.
- s. Nasopharyngeal swab will be used for influenza Subtype RT-PCR, qRT-PCR, quantitative culture and may also be used for rapid influenza diagnosis; Will also be used for viral genotyping and phenotyping if needed and multiplex PCR assay.
- t. Nasal swab collected for influenza diagnostic test or other local test for influenza diagnosis

- u. BAL samples (for biomarkers) are requested only if the procedure/sampling is being carried out for routine management of the patient and at any timepoint throughout the study
- v. Endotracheal aspirates (biomarkers/neutrophil counts) are required for subjects who are intubated.
- w. Nasal samples for biomarkers will be collected at the days indicated from all subjects using nasal SAM strips.
- x. An optional procedure, nasal wash, will be used to collect nasal samples from as many non-intubated subjects as feasible.
- y. PK samples will be drawn on Day 1 (pre-dose), Days 3 and 5 to coincide with PD measurements (nasal washes if done, endotracheal samples and a blood draw for exploratory biomarkers). In sentinel cohort 1 (less severe subjects with normal renal function), PK samples will be additionally drawn on Day 3 at pre-dose, and 0.5, 1 (end of infusion), 1.5, 2, 3, 4, 8 and 12 hours post-dose. **Note: PK draws must be collected from the opposite arm from the infusion arm.**
- z. Informed consent for optional substudies (e.g., genetic research and transcriptomics), must be obtained before collecting samples. In subjects who consent, a blood sample for genetic research is collected at the baseline visit, or at the earliest point possible during the treatment period for genetic research testing; blood samples for transcriptomics are taken on each of the indicated days and used to evaluate changes in transcriptome profiles.

Table 4 Time and Events Table: Post-Treatment and Post-Discharge Assessments

Procedures	Post-Discharge Visits/TCs and Assessments Outpatient ^a					
	PT Day 3 (Visit)	Study Day 8 (TC)	Study Day 15 (TC)	Study Day 22 (TC)	Study Day 30 (TC)	Study Day 45 (Visit)
Safety/Efficacy Assessments						
Adverse events	X	X	X	X	X	X
Concomitant medications	X	X	X	X	X	X
Brief Physical Exam	X					X
Complications of influenza / associated antibiotic use ^b	X	X	X	X	X	X
Temperature	X	X	X	X	X	X
Other Vital signs (HR, BP, respiratory rate, oxygen saturation, ventilation status) ^c	X					X
Flu PRO ^d	Daily through Day 14	Daily through Day 14	X	X	X	X
Katz Activities of Daily Living ^e	X	X	X	X	X	X
Activity level ^f	Daily through Day 14	Daily through Day 14	X	X	X	X
Laboratory Assessments						
Clinical chemistry including LFTs ^g (Local+Central)	X					X
Serum Creatinine ^h (Local+Central)	X					X
Hematology ⁱ (Local+Central)	X					X
Pregnancy test ^j	X					
Nasopharyngeal swabs	X					
Exploratory Biomarkers (Blood Sample) ^k	X					X
Transcriptomics (blood sample) ^l	X					X
Nasal SAM strips (biomarkers) ^m	X					X
Nasal washes ⁿ	X					X
Hospital Readmission Status	X	X	X	X	X	X

a. Following discharge from hospital, outpatient clinic visit/TC schedule of assessments will be followed for those patients who are discharged before Day 45. For 5 days treatment, PT Day 3 will be the same as Day 8 and will be a clinic visit.

- b. Complications of influenza such as bacterial pneumonia, pneumothorax, pleural effusion, ARDS, myositis, encephalitis, myocarditis, and associated antibiotic use will be recorded on all assessment days.
- c. Vital signs and ventilation status will be assessed at clinic visits (PT Day 3 and Day 45).
- d. FLU PRO to be measured once daily through Study Day 14.
- e. Activities of Daily Living (Katz Scale) to be done at clinic visits and at TCs.
- f. Activity level assessed by reporting on a 3 point scale of bed rest (1), limited ambulation (2) or unrestricted (3) to be done daily through Study Day 14.
- g. Clinical chemistry including LFTs to be required once every other day until PT Day 3 (for LFTs, local testing for subject management until PT Day 3; central testing for all assessments, including at Day 45).
- h. Serum creatinine required once every day until PT Day 3 (local testing for subject management until PT Day 3; central testing for all assessments, including at Day 45).
- i. Hematology panel including CBC with differential required once every other day until PT Day 3 (local testing for subject management until PT Day 3; central testing for all assessments, including at Day 45).
- j. Ultrasensitive urine pregnancy test required in women of childbearing potential on PT Day 3.
- k. Blood samples will be collected for exploratory biomarkers at PT Day 3, and at Study Day 45.
- l. Blood samples for transcriptomics will be collected on PT Day 3 and Study Day 45 and are optional. Samples will be collected only from those subjects who provide informed consent for genetic research.
- m. Nasal samples for biomarkers will be collected at PT Day 3 and Study Day 45 from all subjects using nasal SAM strips. In addition, an optional procedure, nasal wash, will be used to collect nasal samples from as many non-intubated subjects as feasible.

